5.4.7 Pharmacokinetic Set

The Pharmacokinetic (PK) set will include all randomized subjects within the PK Sub-study strata who received at least one dose of Rifaximin. The PK set will be defined with approval from Alfasigma after receipt of plasma concentration data, database lock and unblinding.

PK set will include all subjects who have received at least 1 dose of IMP and, specifically that they satisfy the following criteria for at least 1 profile:

- · No missing samples at potential critical time points.
- No relevant events (e.g. protocol deviations or adverse events) that may impact the study objectives with respect to the PK endpoints.
- Subjects who received placebo will not be included in the PK population.

5.5 Baseline Definition

Baseline is defined as the last non-missing assessment prior to the first administration of study medication (including unscheduled assessments) in the study.

5.6 Derived and Transformed Data

Variables requiring calculation will be derived using the following formulas:

- Days A duration expressed in days between a date (date1) and another later date (date2) will be calculated using the following formula:
 - duration in days = date2 date1 + 1
- Months A duration expressed in months is calculated as the number of days divided by 365.25/12 (approximately 30.4)
- Years A duration expressed in years is calculated as the number of days divided by 365.25
- Change from baseline will be calculated as:

Change = post baseline value - baseline value

5.7 Subgroups

The following subgroup analyses will be performed:

5.7.1 Co-primary endpoints

The co-primary endpoints will be analysed by the following subgroups:

- Stratification factor: L-BT Positive, L-BT Negative
- Breath H2 concentrations at Screening (increase of ≥20 ppm of H2 within 90 minutes compared to baseline, increase of <20 ppm of H2 within 90 minutes compared to baseline)
- Breath CH4 concentrations at Screening (increase of > 10 ppm of CH4 within 90 min, increase of ≤10 ppm of CH4 within 90 minutes compared to baseline)

Treatment effect within subgroups will be presented by descriptive statistics (including 95%CI), inferential analysis and forest plots.

5.7.2 Secondary efficacy endpoints

All secondary endpoints will be analysed by stratification factor.

The following secondary endpoints will be analysed by Breath CH4 concentrations (increase of> 10 ppm within 90 min compared to baseline, increase of \leq 10 ppm within 90 minutes compared to baseline) at Screening:

- Mean change from Baseline in number of inflammatory lesions at Day 60
- Percent of participants showing treatment success (i.e. IGA score of 0 or 1)
- Percent of participants with IGA score of 0 (clear)

Treatment effect within subgroups will be presented by descriptive statistics (including 95%CI) and inferential analysis.

5.8 Visit Windows

No visit windows will be applied for this study.

5.9 Missing Data

Summary statistics will generally be reported based upon observed data. Should a determination of treatment period (on treatment, pre-treatment) be required for adverse events or concomitant medications but the corresponding date is missing, or is a partial date, the event/medication will be considered on-treatment unless the portions of the date that are available indicate this is not possible.

Rules for imputation of start dates for AEs, concomitant medications and safety assessments are outlined in Table 6. Rules for imputation of end dates for AEs and concomitant medications are outlined in Table 7. Any AEs, concomitant medications and safety assessments with partial/missing dates will be displayed as such in the data listings.

Table 6: Imputation of start dates (AE, concomitant medications) and safety assessments (laboratory data, vital signs)

Missing	Rule
element	
year, or entire date	No imputation.

Missing	Rule		
element			
day, month	If available year = year of study treatment start date then		
	If stop date contains a full date and stop date is earlier than study treatment start date then set start		
	date = 01JanYYYYY		
	Else set start date = study treatment start date.		
	If available year > year of study treatment start date then 01JanYYYY. If available year < year of study treatment start date then 01JulYYYY.		
day	If available month and year = month and year of study treatment start date then		
	If stop date contains a full date and stop date is earlier than study treatment start date then set start		
	date= 01MMMYYYY.		
	Else set start date = study treatment start date.		
	If available month and year > month and year of study treatment start date then 01MMMYYYY.		
	If available month and year < month year of study treatment start date then 15MMMYYYY.		

Table 7: Imputation of end dates (AE, concomitant medications)

Missing	Rule	
element		
year, or entire	No imputation.	
date	Notes:	
	 If the AE or medication is ongoing, the stop date will remain missing. 	
	 The AE or medication will be included in all relevant time interval categories from its start day. 	
day, month	If partial end date contains year only, set end date = earliest of 31DecYYYY or end date of the study	
day	If partial end date contains month and year, set end date = earliest of last day of the month or er	
	of the study	

With reference to efficacy analyses performed on the FAS, the last observation carried forward (LOCF) strategy will be employed for dealing with any missing continuous post-baseline data for the relevant primary and secondary endpoints. For binary data (i.e. Success/Failure) missing data will be considered as Failures, unless differently specified in the appropriate analysis section for that data.

With reference to other categorical variables, the number of patients with missing data will be presented under the "unknown" category. Missing values will be included in the denominator count when computing percentages, unless differently specified in the appropriate analysis section for that data.

LOCF imputation will be used for the inferential analysis of categorical variables.

When other continuous data will be summarized, only the non-missing values will be evaluated for computing summary statistics.

Missing data in safety variables will not be imputed/replaced unless otherwise specified in the analysis section.

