10.8 Prior and Concomitant Therapy

Prohibited Treatment

Initiation of beta-blocker treatment is not allowed from the screening visit (V1) to the end of followup (Day 60; V4) included. Patients already on chronic treatment with beta-blockers at the screening visit can be enrolled in the study.

Initiation of any oestroprogestinic or progestogen contraceptive or oestroprogestinic or progestogen replacement therapy is not allowed from V1 to V4 included. Patients already treated with oestroprogestinic or progestogen contraceptives or oestroprogestinic or progestogen replacement therapy before V1 can be enrolled in the study.

The following medication will not be permitted from V1 to V4 included:

- Biologic or non-biologic immunomodulatory or immunosuppressive drugs; warfarin (or other coumarins); niacin; topical facial or systemic antibiotic treatments; neomycin or any other low-absorbable oral antibiotics (such as marketed rifaximin); topical facial, inhaled or systemic corticosteroids; topical and systemic retinoids; any other topical or systemic treatment for rosacea (including also laser and pulsed light, etc.).
- Any cancer-related treatment.
- "Over the counter" formulations including intestinal and topical skin probiotics.

• Any other experimental treatment

Concomitant Permitted Treatments

All other medications for concomitant chronic conditions are allowed and should be maintained constant throughout the whole study.

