6.6 Concomitant Medications

Medications will be considered as prior if they stopped before the first study drug intake.

Prior and concomitant medications will be coded using the World Health Organization Drug Dictionary (WHO-DD) and will be classified according to the default Anatomical Therapeutic Chemical (ATC) classification system code (up to 4 levels), WHO-DD Drug Name, and Preferred Term (PT).

Prior and concomitant medications will be summarized separately for the SAF by the ATC Class Level 1 category, Level 2 category and PT. Subjects may have more than one medication per ATC category and PT. At each level of subject summarization, a subject will be counted once if he/she reports one or more medications at that specific level. The prior medication frequency distribution table will be displayed by the safety treatment arms and all subjects even though the prior medication information was collected prior to dispensing study drug.

Additionally, prohibited concomitant medications will also be summarized.

Prohibited concomitant medications from V1 to V4 include:

- Initiation of beta-blocker treatment (ATC = C07)
- Initiation of any oestroprogestinic or progestogen contraceptive or oestroprogestinic or progestogen replacement therapy (ATC = G03 [excluding G03XB], G02B)

- Biologic or non-biologic immunomodulatory or immunosuppressive drugs (ATC = L); warfarin (or other coumarins) (ATC = B01AA); niacin (ATC=A11HA); topical facial or systemic antibiotic treatments (ATC = J01, D01, D06); neomycin or any other low-absorbable oral antibiotics (such as marketed rifaximin) (ATC = A01AB, B05CA, J01GB, R02AB, A07A); topical facial, inhaled or systemic corticosteroids (ATC = D07, H02, A01AC, A07EA, D10AA, M01BA, N02CB, R01AB, R01AD, R03AK, R03AL, R03BA); topical and systemic retinoids (ATC = D05BB, D10AD, D10BA, L01XF); any other topical or systemic treatment for rosacea (including also laser and pulsed light, etc.) (ATC = D).
- Any cancer-related treatment (ATC = L).
- "Over the counter" formulations including intestinal and topical skin probiotics (ATC=A07F).
- Any other experimental treatment.

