8.1 Adverse Events

Adverse events will be presented for the Safety Analysis Set (SAF), by treatment group.

All adverse events will be assigned to a Preferred Term (PT) and will be classified by Primary SOC according to the latest MedDRA version.

Any adverse event which started at or after the first administration of study treatment will be considered as Treatment Emergent Adverse Event (TEAE). If the start date is missing for an AE, the AE will be considered to be treatment emergent. See Section 5.9 for details on partially missing AE start dates.

Adverse events will be reported on a per-patient basis. This means that even if a patient reported the same event repeatedly, the event will be counted only once. Also, the number of events will be presented.

TEAEs relationship to study medications and TEAE severity will be investigated with frequency tables.

In case of missing relationship/severity, the AE is considered related/severe, respectively.

The following tables will be presented:

- Overview of TEAEs showing the number of TEAEs, the number of TESAEs and the number of
 patients with any TEAEs, treatment-related TEAEs, serious TEAEs, treatment-related serious
 TEAEs, severe TEAEs, TEAEs leading to treatment discontinuation and TESAEs with Outcome
 equal to Death;
- 2. Summary of TEAEs by Primary SOC and PT;
- Summary of Related TEAEs by Primary SOC and PT;

- 4. Summary of TEAEs by Primary SOC, PT and maximum Severity;
- 5. Summary of Serious TEAEs by Primary SOC and PT;
- 6. Summary of Related and Serious TEAEs by Primary SOC and PT;
- 7. Summary of Serious TEAEs by Primary SOC, PT and maximum Severity;
- Summary of TEAEs Leading to Early Discontinuation of the Study Treatment by Primary SOC and PT.
- 9. Summary of TEAEs Leading to Temporary Interruption by Primary SOC and PT.
- 10. Summary of Most Frequent AEs (at least 2% in any treatment group) by PT

No inferential statistical tests will be applied to compare the treatment arms in terms of incidence of adverse events.

By-patient listings will be created for the following:

- 1. All Treatment Emergent Adverse Events
- 2. Serious Treatment Emergent Adverse Events
- 3. Treatment Emergent Adverse Events Leading to Treatment Discontinuation or Temporary Interruption
- 4. All Treatment Emergent Adverse Events in Patients with Fatal TEAEs

Adverse events occurred before the first administration of study treatment will only be listed.

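### SAP Table 6 and SAP 8.1 can count an adverse event that ended before first dose as treatment-emergent, against the SAP's own rule on incomplete dates

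*SAP*

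**What the plan says.** SAP 5.9 first gives a general rule. Where the treatment period of an adverse event or medication must be decided and its date is missing or partial, the item is "considered on-treatment unless the portions of the date that are available indicate this is not possible".

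Table 6 then imputes start dates for adverse events, medications, laboratory data and vital signs:

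- Partial start in the same year (or same month and year) as first dose: the start goes to 1 January (or the first of the month) "If stop date contains a full date and stop date is earlier than study treatment start date". Otherwise: "Else set start date = study treatment start date".
- Partial start in an earlier year: 1 July of that year. In an earlier month: the 15th of that month. Neither branch refers to the stop date.
- Year or whole date missing: no imputation.

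Table 7 imputes a stop date with only the day missing as the last day of the month, or end of study if earlier.

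SAP 8.1 defines a treatment-emergent event (TEAE) as one starting at or after first administration, and adds: "If the start date is missing for an AE, the AE will be considered to be treatment emergent". It refers to 5.9 for partly missing start dates.

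Three other provisions bear on the safeguards. SAP 6.6 lists as prohibited "Initiation of beta-blocker treatment (ATC = C07"). Protocol 10.8 says: "Patients already on chronic treatment with beta-blockers at the screening visit can be enrolled in the study". SAP 5.5 defines baseline as the "last non-missing assessment prior to the first administration of study medication".

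**The concern.** The general rule lets known date parts exclude an item from the treatment period. Table 6 uses the stop date for that purpose only if it is complete. SAP 8.1 does not use the stop date at all when the start is missing. An event whose recorded dates show that it was over before dosing can therefore enter the TEAE tables, and the derived data can hold an event that ends before it begins. Adverse events are collected from consent at V1, up to 30 days before dosing, so pre-dose events can exist in the database.

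**Working it through.** No sample size, power or alpha figure is involved, and the plan states no figure to reproduce. The check applies Tables 6 and 7 as written.

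**Worked cases.** Assumed dates: V1 14 March 2022, first dose 10 April 2022.

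| Recorded start | Recorded stop | Table 6 start | Stop after Table 7 | TEAE? | Start after stop? |
|---|---|---|---|---|---|
| 2022 | Mar 2022 | 10 Apr 2022 | 31 Mar 2022 | yes | yes |
| 2022 | 25 Mar 2022 | 1 Jan 2022 | 25 Mar 2022 | no | no |
| Mar 2022 | Mar 2022 | 15 Mar 2022 | 31 Mar 2022 | no | no |
| Mar 2022 | 10 Mar 2022 | 15 Mar 2022 | 10 Mar 2022 | no | yes |
| Apr 2022 | Apr 2022 | 10 Apr 2022 | 30 Apr 2022 | yes | no |

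Row 1 is the contradiction: the latest possible stop is 31 March, before first dose, yet the event is a TEAE. Row 4 gives an impossible date but the right class. Row 5 is the conservative default working as intended, because April to April does not exclude treatment.

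**Missing start.** With no start date, Table 6 imputes nothing and 8.1 makes the event a TEAE. A recorded stop of, say, 25 March 2022 does not change that, although an event over by 25 March cannot have started on or after 10 April.

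**How narrow the Table 6 fault is.** Take adverse events lying wholly within the 30 days before first dose. Enumerate 365 first-dose dates in 2022, start lags of 1 to 30 days, and every duration that ends before dosing, all equally weighted (an assumption). That gives 365 × (1 + 2 + … + 30) = 365 × 465 = 169,725 cases per pattern of known date parts.

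| Start known to | Stop known to | Counted as TEAE | Counted as TEAE although the date parts prove otherwise |
|---|---|---|---|
| month | day | 0% | 0% |
| month | month | 33.2% | 0% |
| month | year | 33.2% | 0% |
| year | day | 0% | 0% |
| year | month | 94.4% | 32.1% |
| year | year | 94.4% | 0% |

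Only one of the six patterns breaks the 5.9 rule. If the Table 7 end date is used in the Table 6 test, row 1 of the worked cases gets start 1 January 2022, and the 32.1% falls to 0%. These are shares of records that already have the pattern, not shares of patients.

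**Medications and laboratory data, same dates.** An ongoing beta-blocker with start 2022 is dated 10 April. Start March 2022 gives 15 March, one day after V1. Start February 2022 gives 15 February and start 2019 gives 1 July 2019, both before V1. A V1 laboratory result dated April 2022 goes to 10 April (Day 1), while one dated March 2022 goes to 15 March. With the V1-to-dose lag spread evenly over 1 to 30 days, 49% of day-missing V1 results move to Day 1; over 1 to 14 days, 75%. A day-missing V3 result lands on Day 1 in about 5% of cases (draws 28 to 30 days after first dose).

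**The case against.** **Such records will hardly exist.** Protocol 15.1.6 requires onset and resolution dates, Protocol 17.10 provides for validation checks and queries, and screening lasts at most 30 days. An unknown month for a screening event is barely plausible. This stands, and it limits the size of the point.

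**Counting doubtful events as treatment-emergent is a deliberate conservative convention.** Protocol 16.3.4 has the same sentence on missing start dates. This stands wherever the dates leave the matter open, as in most of the six patterns. It does not cover an event whose stop date settles the matter.

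**The general sentence in 5.9 may refer only to parts of the start date itself.** That reading is possible, but Table 6 already lets a full stop date decide. A TEAE that ended before dosing also fails the definition in 8.1.

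**The general sentence might override the table.** Perhaps, but the SAP does not say which prevails.

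Three stronger readings are tempting, and the documents do not support them.

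- *Any pre-treatment event with a partial stop date becomes a TEAE.* Start and stop both March 2022 do not, and in most other patterns the dates prove nothing.
- *Permitted chronic use of a beta-blocker or hormonal therapy becomes a prohibited initiation and costs per-protocol membership.* SAP 6.6 never says that imputed dates define initiation. SAP 6.3 assesses deviations on available data before lock, listings show partial dates as recorded, and medications are taken at V1 with only changes at V2. Most long-standing use would in any case be dated before V1.
- *A patient loses laboratory baseline.* That requires Day 1-dated values to be rejected. The V2 lesion counts and vital signs are Day 1 assessments and must qualify as baseline, so a program that accepts Day 1 values would keep the result.

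**Conclusion.** The point holds as an internal contradiction with three parts. First, a year-only start in the treatment year with a month-and-year stop before the month of first dose yields a TEAE that ends before it starts. Second, an event with no start date and a stop date before first dose is a TEAE under 8.1. Third, the 15th-of-month and 1 July branches can date a start after the stop, which is an impossible date but not a TEAE.

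The point is minor. How often these date patterns occur is unknown, and the enumerated percentages rest on equal weights. The outputs affected are descriptive safety tables, on which no inferential tests are planned.

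The medication and laboratory consequences are conditional. They arise only if imputed dates drive the prohibited-medication flag and the choice of baseline, which the SAP does not state. The laboratory case deserves a sentence because V1 is the only scheduled pre-dose draw. Accepting Day 1 by date alone is not fully safe either, since a day-missing V3 result can also land there.

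**What to change.** 1. SAP 5.9, Table 6: replace the full-stop-date condition with a test of whether the full stop date, or the end date imputed by Table 7, is before first dose.
2. SAP 5.9, Table 6: add that no imputed start may be later than the full or imputed stop date. This repairs the 15th-of-month and 1 July branches, which change 1 leaves untouched.
3. SAP 8.1: after the sentence on missing start dates, add an exception for events whose full or imputed stop date is before the first dose. Protocol 16.3.4 has the same sentence, so list this change in SAP section 10.
4. Safeguards: state in SAP 6.6 that a drug recorded as in use at V1 is not an initiation, whatever its imputed start. State in SAP 5.9 that laboratory and vital-sign records with a partial date are assigned to their nominal visit, so that a V1 laboratory value stays eligible as baseline. This fits SAP 5.8, which applies no visit windows.

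The cost is a few lines of SAP text and a small programming change. No new data are needed.

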16.3.8 Handling of Missing and Incomplete Data

Summary statistics will generally be reported based upon observed data. Should a determination of treatment period (on treatment, pre-treatment) be required for adverse events or Lactulose medication but the corresponding date is missing, or is a partial date, the event/medication will be considered on treatment unless the portions of the date that are available indicate this is not possible. With reference to the statistical analyses performed on the FAS, the last observation carried forward (LOCF) strategy will be employed for dealing with any missing continuous data for the relevant primary and secondary endpoints. For categorical data (i.e. Success/Failure) missing data will be considered as Failures, unless differently specified in the SAP.

With reference to other categorical variables, the number of patients with missing data will be presented under the "unknown" category. Missing values will be included in the denominator count when computing percentages, unless otherwise specified in the SAP.

When other continuous data will be summarized, only the non-missing values will be evaluated for computing summary statistics.

Missing data in safety variables will not be replaced.

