4.1 General Study Design and Plan

Subjects will be offered participation to the PK sub-study. If they agree, and have a suitable PK profile, they will be randomized according to the relevant stratum; otherwise, they will enter the main study.

Subjects will be dispensed blinded investigational product according to the randomization schedule. Investigational product will be dispensed at the Day 1 (Randomization) visit; at this visit, each eligible subject will receive a patient's kit containing two "treatment bottles", covering the treatment necessary for 30 days of study. All tablets are identical in appearance and the strengths are placebo and 250 mg. Subjects will be instructed to take 2 tablets of investigational product three times daily (TID) by mouth, in order to maintain study blinding. For the 250 mg TID dose groups this comprises one active and one placebo tablet. For the 500 mg TID dose group, this comprises two 250 mg tablets. For the placebo dose group, this comprises two placebo tablets. TID doses of the assigned treatment will be administered from Day 1 to Day 29. On Day 30 just the first daily dose will be administered.

There will be 3 study drug treatment arms:

- Two tablets of Rifaximin-EIR 250 mg formulation TID (1500 mg daily) for 29 days; on Day 30 subjects will receive two tablets of Rifaximin-EIR 250 mg in single administration (500 mg).
- One tablet of Rifaximin-EIR 250 mg formulation TID (750 mg daily) + one tablet of placebo TID for 29 days; on Day 30 subjects will receive one tablet of Rifaximin-EIR 250 mg and one tablet of placebo in single administration (250 mg).
- Two tablets of placebo TID for 29 days; on Day 30 subjects will receive two tablets of placebo in single administration.

For subjects included in the PK sub-study the first drug intake must be performed at the investigational site in occasion of the randomization visit (Day 1), immediately after the first blood draw (for PK analysis) and preferably early in the morning (approximately 8:00 a.m.). Also, at Day 30 subjects participating in the PK sub-study will stay overnight at the center to complete the PK procedures.

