5.4.4 Full Analysis Set

The primary efficacy analysis population will be the Full Analysis Set (FAS), defined as all randomized patients having taken at least one dose of the investigational treatment and have at least one post baseline assessment for any of the two co-primary endpoints.

To mitigate the impact of the treatment kit misallocations, the primary statistical analysis on the FAS will be performed according to the actual treatment received (not according to the "randomized" treatment, as per ITT principle).

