7.2 Primary Efficacy Analyses

The co-primary efficacy endpoints, clinically assessed by the Investigator, are the change from baseline in total number of rosacea inflammatory lesions (papules and pustules) at the end of treatment, and the percent of subjects showing treatment success, defined as an IGA score of 0 (clear) or 1 (almost clear) with at least a 2-grade improvement from baseline at the end of treatment.

The first co-primary efficacy endpoint (change from baseline in number of inflammatory lesions at end of treatment (Day 30)) will be analyzed by means of an Analysis of Covariance (ANCOVA) model (one model for each comparison to placebo), with change from Baseline to Day 30 as dependent variable, treatment group and L-BT status at screening as explicative factors, and baseline number of inflammatory lesions as covariate.

The adjusted mean differences with the corresponding 95% confidence interval will be estimated from the model. The 95% confidence interval for the difference between adjusted mean differences of each active treatment arm versus the placebo arm will be also presented.

The second co-primary efficacy endpoint (percent of patients showing treatment success) will be analyzed by means of a stratified (by L-BT status) Cochran Mantel-Haenszel (CMH) chi square test. The Breslow- Day test with Tarone's adjustment for stratified tables will be applied. A two-sided 95% CI for difference in success rate between the treatment groups (each active group vs placebo) overall and by L-BT status will also be computed.

For each co-primary endpoint, inferential statistical analyses will be completed for each subgroup described in Section 5.7.

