7.3 Secondary Efficacy Analyses

Considering the explorative nature of the secondary endpoints, all the inferential results obtained on them will be descriptively interpreted.

7.3.1 Change from Baseline in number of inflammatory lesions (papules and pustules) at end of study (Day 60)

The change from baseline to V4 will be analyzed by means of an Analysis of Covariance (ANCOVA) Model (one model for each comparison to placebo), with change from Baseline to Day 60 in inflammatory lesions as dependent variable, treatment group and L-BT status at screening as explicative factors and baseline count of inflammatory lesions as covariate.

The adjusted mean differences with the corresponding 95% confidence interval will be estimated from the model. The 95% confidence interval for the difference between adjusted mean differences of each active treatment arm versus the placebo arm will be also presented.

7.3.2 Percent of participants showing treatment success (i.e. IGA score of 0 or 1) at end of treatment (Day 30) and end of study (Day 60).

The percent of participants showing treatment success (IGA score of 0 or 1) at the end of treatment (Day 30) and end of study (Day 60) will be separately analyzed by means of a two-sided Cochran Mantel-Haenszel Chi-square test stratified by L-BT status at screening. The Breslow-Day test with Tarone's adjustment for stratified tables will be applied. A two-sided 95% CI for difference of success rate between the treatment groups (each treatment arm vs placebo) will also be computed.

7.3.3 Percent of participants with IGA score of 0 (clear) at end of treatment (Day 30) and end of study (Day 60)

The percent of participants with an IGA score of 0 at the end of treatment (Day 30) and end of study (Day 60) will be separately analyzed by means of a two-sided Cochran Mantel-Haenszel Chi-square test stratified by L-BT status at screening. The Breslow-Day test for stratified tables will be applied. A two-sided 95% CI for difference of success rate between the treatment groups (each treatment arm vs placebo) will also be computed.

7.3.4 Change from Baseline in additional rosacea features at end of treatment (Day 30) and end of study (Day 60)

The following rosacea features will be analyzed:

- 1. Pain, burning/stinging and itching (measured using a 0-10 cm Visual Analogue Scale (VAS))
- 2. telangiectasia (absent=0, mild=1, moderate=2, severe=3)
- 3. ocular manifestations (absent=0, mild=1, moderate=2, severe=3)

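### LOCF is the only planned handling of missing lesion counts, and on this visit schedule it can shift both the Day 30 and the Day 60 treatment difference

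*SAP*

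**What the plan says.** SAP 5.9 states that for FAS efficacy analyses "the last observation carried forward (LOCF) strategy will be employed for dealing with any missing continuous post-baseline data" in the primary and secondary endpoints. Protocol 16.3.8 has the same rule: "With reference to the statistical analyses performed on the FAS, the last observation carried forward (LOCF) strategy will be employed". Responder endpoints are handled differently: "For binary data (i.e. Success/Failure) missing data will be considered as Failures" (SAP 5.9).

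The LOCF rule reaches two lesion-count analyses. One is the co-primary ANCOVA, "with change from Baseline to Day 30 as dependent variable" (SAP 7.2). The other is the secondary ANCOVA, "with change from Baseline to Day 60 in inflammatory lesions as dependent variable" (SAP 7.3.1).

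Post-baseline counts are scheduled only at V3 (Day 30 ± 1) and V4 (Day 60 ± 3). An early termination visit (ETV) with a count may fall on any day from 1 to 60, and an unscheduled visit includes a count if the investigator thinks it necessary (Protocol 11.1, 11.2.8, 11.2.9; SAP 4.4.2). SAP 5.8 applies no visit windows. Treatment stops at V3: "On Day 30 just the first daily dose will be administered" (SAP 4.1).

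The SAP's FAS takes dosed patients who "have at least one post baseline assessment for any of the two co-primary endpoints" (SAP 5.4.4). SAP 7.1 names two sensitivity analyses for the primary analysis, by randomized treatment on the FAS and on the mFAS. Both address the kit misallocation.

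**The concern.** LOCF is hard to defend when there is little to carry and the treatment state changes between visits. Three situations arise here.

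- **Exit before Day 30.** The only post-baseline counts available are from an ETV or unscheduled visit. With no visit windows, a count from the first days of dosing can stand in for the Day 30 value.
- **V3 seen, no later count.** The end-of-treatment count becomes the Day 60 result, about 30 days off drug. That assumes the benefit persists, which is what the Day 60 comparison is meant to examine.
- **V4 seen, V3 missed.** Reading the FAS condition as any post-baseline lesion count or IGA, this patient is in the FAS. There is no scheduled post-baseline count to carry to Day 30, and the SAP gives no rule.

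One of the two co-primary estimates thus depends on an assumption about missing data that the plan never varies.

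**Working it through.** **The plan's own dropout figure.** Protocol 16.1 gives 51 per arm before dropout and about 10% dropout. 100 × 51 / (100 − 10) = 56.67, rounded up to 57; 57 × 3 = 171. This reproduces the stated total. At the final 67 per arm, 10% is 67 × 0.10 = 6.7 patients per arm.

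**Assumed inputs.** The effect size, SD and power are not readable in the public text. I assume a Day 30 effect E30 of 4 lesions in the lesion-scale examples. On the SD scale I take what 51 per arm detects at 80% or 90% power: (1.960 + 0.842) × √(2/51) = 0.555 SD, or (1.960 + 1.282) × √(2/51) = 0.642 SD. The standard error with 67 per arm is √(2/67) = 0.173 SD. Patients who leave are assumed to have the same true mean course as those who stay.

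**Day 60, equal dropout d after V3 with no later count.** Let r be the share of E30 retained off drug.

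- True difference: r·E30. LOCF difference: (1 − d)·r·E30 + d·E30. Overstatement: d(1 − r)·E30.
- At d = 0.10: r = 1 gives 0; r = 0.5 gives 0.05·E30; r = 0 gives 0.10·E30. For 4 lesions these are 0, 0.2 and 0.4. At d = 0.20 and r = 0 the figure is 0.8.
- If the effect is wholly lost (r = 0) at d = 0.10, the bias is 0.055 or 0.064 SD, and a nominal 5% test rejects 6.2% or 6.6% of the time. At d = 0.20 it rejects 9.8% or 11.5%.

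**Day 30, equal dropout d.** Let f be the share of the Day 30 change already reached at exit.

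- LOCF difference: E30 × [1 − d(1 − f)]. At d = 0.10 the effect is understated by 0% (f = 1), 5% (f = 0.5) or 10% (f = 0).
- With 67 per arm and E30 = 0.555 SD, power is 89.5%, 86.2% and 82.4% respectively (normal approximation, SD unchanged).

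**Day 30, unequal dropout.** Assume mean changes of −12 (active) and −8 (placebo), a true difference of −4, with one third of the change carried at exit. Each arm's LOCF mean is its change × (1 − d × 2/3).

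| Dropout, active / placebo | Active | Placebo | Difference |
|---|---|---|---|
| 5% / 15% | −12 × 0.9667 = −11.6 | −8 × 0.90 = −7.2 | −4.4 |
| 15% / 5% | −12 × 0.90 = −10.8 | −8 × 0.9667 = −7.73 | −3.1 |
| 10% / 10% | −12 × 0.9333 = −11.2 | −8 × 0.9333 = −7.47 | −3.7 |

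These figures depend on the assumed placebo change. With no placebo change (active −4) the two unequal cases give −4 × 0.9667 = −3.9 and −4 × 0.90 = −3.6, both attenuated.

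**Day 30 under no treatment effect.** With a common improvement of c SD, the bias is (d_placebo − d_active) × c × (1 − f). Equal dropout and equal courses give zero. Dropout of 5% against 15%, with c from 0.5 to 1 and f from 0 to 0.5, gives 0.025 to 0.10 SD, in a direction set by which arm loses more. The nominal 5% test then rejects 5.2% to 8.9% of the time.

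**The case against.** The strongest reply is that the consequence is small in an exploratory phase IIa trial. Much of it stands.

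- **Certainty.** A reader might infer that LOCF necessarily biases both endpoints, or favours the drug. The documents do not support that. Bias is zero at Day 60 if the effect persists, and zero at Day 30 if counts at exit already equal the Day 30 value. With equal dropout and a real effect, Day 30 is attenuated. The protocol's background reports that about 65% of remitters in one earlier study were still in remission at three years. That is not evidence for this trial, but it makes total loss by Day 60 an extreme case.
- **Route to Day 60.** A reader might infer that everyone who leaves after V3 carries the Day 30 count. A patient with an ETV between Day 30 and Day 60 carries an off-drug count, so the Day 60 figures above are upper values.
- **Durability.** A reader might take the Day 60 lesion count as the only off-drug test. It is not: IGA 0/1, IGA 0, erythema, telangiectasia, symptom scores and two modified IGA scales are also analysed at V4. SAP 7.3 treats all secondary inference descriptively.
- **Study success.** SAP 3.2.1 requires both co-primaries in an arm, and a missing binary outcome counts as failure. LOCF on the lesion count cannot by itself produce success. (SAP 5.9 also assigns LOCF to inference on categorical variables without saying which; that should be clarified.)
- **Visibility.** Summary statistics are generally on observed data, so a reader can compare observed means. That is not a pre-specified inference under another assumption.

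None of this supplies the missing V4-only rule or a missing-data sensitivity analysis.

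**Conclusion.** The point holds in conditional form. LOCF is the sole method for missing lesion counts on the FAS, it fits this schedule poorly, and no named sensitivity analysis tests it. It can bias the treatment difference; whether it does depends on dropout and on the unobserved course.

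At the planned 10% dropout, equal across arms, the error is at most about 10% of the Day 30 effect: an overstatement at Day 60 if the effect wanes, an understatement at Day 30. For an assumed 4-lesion effect that is 0.4 lesions. Unequal dropout of 5% against 15% moves an assumed −4.0 at Day 30 to −4.4 or −3.1, given mean changes of −12 and −8 and one third of the change carried. Only the 10% dropout, the sample sizes and the visit schedule come from the documents; the rest is assumed. This is a cheap improvement, not a flaw that undermines the trial.

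**What to change.** **Preferred.** Replace LOCF for lesion-count change with multiple imputation by treatment arm (as assigned in each analysis), using baseline count, L-BT status, ETV and unscheduled counts, V3 and V4. Analyse each completed dataset with the planned ANCOVA and combine by Rubin's rules. Keep LOCF as a sensitivity analysis. This covers V4-only patients.

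**Minimum.** Pre-specify that imputation as a sensitivity analysis for Day 30, and report an observed-data or multiple-imputation result for Day 60. State the rule for V4-only patients. Reconcile the FAS definition too: Protocol 16.2.3 requires dosing only, while the protocol synopsis and SAP 5.4.4 add a post-baseline assessment.

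A repeated-measures model on V3 and V4 alone is less suitable, because it drops early exits whose only count is from an ETV or unscheduled visit.

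**Cost.** SAP text and a little more programming; no new data. The method relies on missing-at-random. Few patients will have both an early count and a V3 count, so the SAP must say how early counts enter the model. The gain is small if few counts are missing.
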